## 16.3. Pregnancy

Where a patient becomes pregnant during their involvement in the trial, this must be reported to NCTU using the appropriate form, within 24 hours of the research team become aware of the situation. The pregnancy must be followed until the outcome is known, to determine if an SAE should be reported. Patients who become pregnant should be withdrawn from the trial and, if they are in the intervention arm, have their enalapril stopped immediately. Decisions regarding all other care, including continuation of chemotherapy, rest with the patient's clinical team.

## 16.4. Overdose

Patients who take a deliberate overdose of enalapril should be referred for an emergency assessment and withdrawn from the trial.

Accidental overdose will be defined as accidental ingestion of greater than the planned daily dose of enalapril. Enalapril is not usually dangerous in overdose, although most commonly causes hypotension. Patients who are asymptomatic, without hypotension at 5 hours are unlikely to have significant toxicity. In the trial population, medical assessment is recommended for overdose in the following patients who are treatment naïve or have taken more than their daily therapeutic dose:

- Patients aged over 65 years (who are more at risk of complications)
- Patients who are known to have renal impairment
- Patients on treatment with azathioprine, lithium or potassium
- Patients who have ingested >0.7mg/kg

After accidental overdose, the patient should not take further enalapril until discussion with the trial team at the earliest opportunity. The safety and appropriateness of restarting enalapril, including timing, will be considered at the discretion of the PI. A maximum of 7 days interruption will be permitted.

All overdoses will be recorded in the eCRF and noted in the deviation log. Where an overdose fulfils an SAE, then it will be fully described in the SAE report form and follow SAE reporting guidelines (see section 16.5).

## 16.5. Adverse Event Reporting

All AEs will be recorded in the patients' medical notes and on electronic case report forms. AEs will be recorded from the day of randomisation until the last visit or until withdrawal, with the exception of adverse events considered related to enalapril, which will be followed until resolution, a stable outcome or death.

All AEs will be assessed for severity, causality, and seriousness and expectedness by an Investigator. All events will be reviewed by the Independent Data Monitoring and Ethics Committee (IDMEC) as part of their ongoing assessment of safety.

Patients should be asked about any adverse events at each visit.

Where an AE fulfils the criteria for a reportable SAE as part of this trial, this will be reported immediately to NCTU (within 24 hours of the research team becoming aware of the event) who will inform the Sponsor and Chief Investigator. Should the SAE form be incomplete at the time of the initial report, follow-up information should be provided as it becomes available. The relationship to the IMP should be assessed by the Investigator at the site, and they will also assess expectedness in relation to the approved RSI.

Exceptions for SAE reporting include hospitalisation for:

- Routine treatment or monitoring of the studied indication not associated with any deterioration in condition
- Treatment which was elective or pre-planned, for a pre-existing condition not associated with any deterioration in condition
- Any admission to hospital or other institution for general care where there was no deterioration in condition

In the event that a SUSAR is fatal or life-threatening, the sponsor will inform the MHRA and the REC within 7 days. In the event that a SUSAR is non-life-threatening, the sponsor will inform the MHRA and the REC within 15 days.

All Principal Investigators will be informed of all SUSARs throughout the trial, as they occur.

SAEs and SUSARs should be reported to NCTU within 24 hours

[[contact]](mailto:[contact])

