### 12.2. Withdrawal of participants

Patients may withdraw from the trial at any time if they wish to, without giving reason and without any adverse consequences for their ongoing clinical management. Patients in the intervention arm will need to stop taking enalapril maleate on the day they withdraw, and return all unused drug to the clinical research team.

All patients will be made aware of their right to withdraw from the study, and this information will be included in the patient information sheet.

Patients should be withdrawn from the trial by the clinical team if:

- the patient suffers unacceptable side effects caused by enalapril maleate;
- the patient becomes ineligible between randomisation and commencement of chemotherapy;
- the patient becomes pregnant or there is evidence that a patient fails to use adequate birth control;
- the patient has disease recurrence.

Data and blood samples for troponin assessment collected up to the point of withdrawal will be kept and used in the analysis of the trial.

Patients will be asked upon withdrawal:

- whether further data can continue to be collected from their medical records;
- whether samples collected for future research may still be analysed;
- whether they may be approached in future research connected to the trial.

This information will be captured on a withdrawal form, to be stored in the ISF and a copy of which sent to NCTU (by email), this will also be captured in the eCRF.

Data from patients who withdraw will remain in the overall analysis; however, dependent on the stage of withdrawal, then further patients may be recruited to ensure that the sample size is reached.

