- f) A Transthoracic Echocardiogram (TTE) must be performed at baseline. At the time of the TTE, blood pressure and heart rate should be measured, and recorded. A TTE will also be performed following the end of chemotherapy. Patients planned to receive Herceptin, must have their TTE performed prior to starting this. All TTEs must be transferred to the Core laboratory for analysis as part of the trial.
- g) Four weeks following the last dose of epirubicin.

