##### **14.6.2. Dose evaluation visit 1**

Two to five days after the start of enalapril, the patient should return for a dose evaluation visit. Blood pressure and U&Es should be measured and the patient should be assessed for side effects.

If the patient has systolic BP  $\geq$ 100 mmHg, normal serum potassium (potassium  $<$ 5.5 mmol/L), and stable renal function (serum creatinine  $<$ 30  $\mu$ mol/L increase from baseline over 48-96 hours) then the enalapril dose should be up-titrated to 5mg BD.

If the patient is, in the clinical opinion of the investigator, unlikely to tolerate a higher dose at this point then the dose should remain the same. At the discretion of the investigator, a further assessment at

dose evaluation visit 2 could be made to consider up-titration of enalapril to 5mg BD using the same criteria as above.

If the patient has a  $\geq 30$   $\mu\text{mol/L}$  increase in serum creatinine levels since the last assessment compared to baseline, new hyperkalaemia (potassium  $\geq 5.5\text{mmol/L}$ ), or symptomatic hypotension (SBP  $< 100\text{mmHg}$ ) then enalapril should be permanently discontinued and the patient withdrawn from the study. The patient should be seen again within 7 days to ensure the reasons for withdrawal have resolved to the satisfaction of the investigator.

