#### **14.6.6. End of treatment with enalapril**

Enalapril will be continued during chemotherapy and stopped three weeks following the last epirubicin dose. Any unused drug will be returned to the clinical research team who will return this to Pharmacy for reconciliation.

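### General adverse-event recording ends at withdrawal, the day enalapril stops, and no section requires new-onset events after that day to be recorded

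*Combined protocol and SAP*

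**What the plan says.** **Recording window.** Section 16.5: "AEs will be recorded from the day of randomisation until the last visit or until withdrawal". The sentence goes on to an exception: "with the exception of adverse events considered related to enalapril, which will be followed until resolution, a stable outcome or death". The same section has patients asked about AEs at every visit.

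**Withdrawal.** Section 12.2: "Patients in the intervention arm will need to stop taking enalapril maleate on the day they withdraw". Its reasons for withdrawal by the clinical team include that "the patient suffers unacceptable side effects caused by enalapril maleate". At dose evaluation visit 1 (section 14.6.2), specified creatinine, potassium or hypotension findings lead to permanent discontinuation and withdrawal from the study, followed by a call-back: "The patient should be seen again within 7 days to ensure the reasons for withdrawal have resolved".

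**Completers.** Section 14.6.6: "Enalapril will be continued during chemotherapy and stopped three weeks following the last epirubicin dose". The trial completion visit, where AEs are collected, is set by footnote g of section 13.1: "Four weeks following the last dose of epirubicin".

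**After withdrawal.** Section 18 follows a study-related AE in a withdrawn patient to its outcome. Section 19.8 uses data up to withdrawal, but follows a patient withdrawn because of a trial-related AE until stable. It also allows primary-endpoint data to be collected later with agreement. Section 12.2 asks whether collection from medical records may continue.

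**Analysis.** The Statistical Analysis section (second section numbered 17.1) plans cross-tabulation of AEs and mentions no follow-up time. Adverse reactions to enalapril and adverse events are both secondary outcomes (section 9.3).

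**The concern.** Two clocks stop on the same day for a withdrawn patient: drug intake and general AE recording. A completer is watched for a further week off drug. More importantly, the withdrawal that closes the window can itself be caused by poor tolerance of enalapril. The truncation is therefore informative, and for these reasons for withdrawal it falls on one arm only.

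A patient withdrawn at visit 1 is still due to receive six cycles of chemotherapy. AEs during those cycles are counted in controls but are not required to be recorded in this patient. If enalapril-arm events go uncollected in this way, a table of counts by arm would tend to favour enalapril, and the independent data monitoring committee would see the same incomplete record.

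**Working it through.** **Inputs**

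- Six cycles, 3 weeks apart (section 15.1): 21 days per cycle.
- Minimum enalapril lead-in before cycle 1: 5 days (section 14.6).
- Enalapril stop in completers: 3 weeks after last epirubicin (section 14.6.6).
- Completion visit: 4 weeks after last epirubicin (section 13.1, footnote g).
- Dose evaluation visit 1: 2 to 5 days after starting enalapril (section 14.6.2).
- Assumption: no chemotherapy delay.

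**Step 1: off-drug window in completers.** With cycle 1 day 1 as day 0, the last epirubicin dose is on day 5 × 21 = 105, enalapril stops on day 105 + 21 = 126, and the completion visit is on day 105 + 28 = 133. The window is 133 − 126 = 7 days. Elsewhere the protocol says one month; read as a 30- or 31-day month, the window is 30 − 21 = 9 or 31 − 21 = 10 days.

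**Step 2: off-drug window in withdrawn patients.** Enalapril stop and end of general AE recording coincide, so the window is 0 days, apart from the related-event exceptions.

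**Step 3: total AE time for a visit 1 withdrawal.** Planned time from first enalapril dose is 5 + 133 = 138 days. Recorded: 2 to 5 days, that is 2/138 = 1.4% to 5/138 = 3.6%. Not covered: 138 − 5 = 133 to 138 − 2 = 136 days.

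**Step 4: weight in the arm.** With 85 patients per arm, planned AE time from first dose is 85 × 138 = 11,730 patient-days. Each visit 1 withdrawal removes 133/11,730 = 1.13% to 136/11,730 = 1.16% of it.

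**Step 5: do the other provisions cover new-onset events?**

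| Section | What continues after withdrawal | New-onset AEs required? |
|---|---|---|
| 16.5 exception | Follow-up of AEs judged enalapril-related | Not stated |
| 18 | Follow-up of a study-related AE | Not stated |
| 19.8 | Patient withdrawn for a trial-related AE, until stable; primary-endpoint data with agreement | Not stated |
| 14.6.2 | Visit within 7 days, to check that the reason for withdrawal has resolved | Not stated |
| 12.2 | Question about use of medical records | No rule that AEs or SAEs be taken from them |

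The exceptions depend on an event being known and judged related. A new event that is not collected is never assessed for causality, so it cannot reach them.

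**Step 6: is it one-sided?** Side effects caused by enalapril (section 12.2) and the visit 1 findings (section 14.6.2) can trigger withdrawal only in the enalapril arm. The other reasons in section 12.2, such as recurrence or pregnancy, can arise in either.

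**The case against.** The strongest reply is that the patients who tolerated enalapril worst are those for whom the protocol makes most provision. The exception in section 16.5 qualifies the cut-off and could be read as lifting it for any enalapril-related event, new or known. Section 19.8 follows the patient, not only the event, after withdrawal for a trial-related AE. Visit 1 withdrawals are seen within 7 days, and AEs are to be asked about at each visit. Section 16.1.1 defines an AE in any randomised patient with no end at withdrawal, and the SAE duty starts when the team becomes aware of an event. Where a patient chooses to leave, ending active collection is also a matter of consent.

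Much of this stands. A reader might infer that new events in intolerant patients go wholly unrecorded and unreported; the text does not say that and does not forbid reporting. A reader might also infer that every stop of enalapril closes AE recording. It does not: sections 13.2.9 and 14.6.5 provide for halting the drug or withdrawing treatment without stating that the patient leaves the trial, and a patient who stays in keeps AE recording to the last visit. At visits 2 and 3 (sections 14.6.3 and 14.6.4) similar findings lead to dose reduction and recheck, not mandatory withdrawal.

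What the reply does not supply is any instruction to record a new-onset AE after withdrawal, least of all one not already judged related. Four Trusts could reasonably apply the text differently.

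**Conclusion.** The point holds in this form: general AE recording ends at withdrawal, on the day enalapril stops, and nothing requires new AEs or SAEs after that to be recorded. The off-drug window is 0 days against 7 for completers (9 to 10 on a calendar-month reading), subject to the related-event provisions. For a visit 1 withdrawal, 133 to 136 of about 138 planned days fall outside general recording, assuming the minimum lead-in and no chemotherapy delay.

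Enalapril-arm AE counts may be understated, because intolerance withdrawals occur only there and the cross-tabulation has no stated allowance for follow-up. The size cannot be estimated: the documents give neither the expected number of such withdrawals nor an event rate after stopping. A reader might take the attrition allowance of 170 − 140 = 30 patients (17.6%) as a ceiling. It is a planning figure for both arms and does not bound the number affected. The fuller analysis plan that the protocol promises could allow for follow-up time, but could not recover events never collected.

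This is a cheap improvement to safety capture and comparability. It does not bear on the primary outcome.

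**What to change.** 1. In section 16.5, replace the cut-off at withdrawal. For withdrawn patients who have not refused further data collection, record new AEs and SAEs for at least the 7 days after the last enalapril dose that completers have. For control-arm withdrawals, count the same period from the withdrawal date so that one rule serves both arms.
2. State that AEs are recorded at the existing call-back in section 14.6.2.
3. Where the patient agrees to use of medical records on the withdrawal form (section 12.2), collect SAEs from the notes to the planned completion date.
4. Reconcile sections 12.2, 14.6.2, 16.5, 18 and 19.8 so that they give one rule on what is collected after withdrawal.
5. Report AEs with follow-up time by arm. The 7-day extension equalises the off-drug window but not total follow-up, so this is still needed.

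The change concerns data capture only and leaves the withdrawal and dosing rules as they are. The cost is a short amendment to the text, an AE page at an existing contact or from notes review, and a little more data entry for withdrawn patients.

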#### **16.6. Foreseeable Adverse Event Reporting**

Foreseeable adverse events should be recorded as adverse events within the trial CRF, but do not require reporting as Serious Adverse Events for this trial.

#### **16.7. Notification of deaths**

Only deaths that are assessed to be caused by the IMP will be reported to the sponsor. This report will be immediate.

#### **16.8. Urgent safety measures**

If any urgent safety measures are taken, the CI/sponsor or NCTU shall immediately and in any event no later than 3 days from the date the measures are taken, give written notice (in the form of a substantial amendment) to the MHRA and the REC of the measures taken and the circumstances giving rise to those measures.

## 17. Statistics

### 17.1. Sample Size

Audit data from 36 patients and 143 samples, showed a positive troponin T in 47% of patients who received  $>300\text{mg/m}^2$  of anthracycline in a six-cycle regimen. As a sensitive marker of cardiac cell death, we expect troponin to be “turned off” if enalapril is effective. There are other potential causes of an elevated troponin during chemotherapy that are accounted for in the sample size calculation. There is clinical consensus that a rate of 20% in elevated troponin would fully account for other causes such as infection.

Assuming alpha of 5%, and 90% power, 140 patients are needed to detect a reduction in the proportion of patients with cardiac troponin T present from 47% to 20% using a two-sided Fisher's exact test.

There is consensus within the clinical community that, a large effect size will be necessary to convince the clinical community to change the pathway of care for these patients.

Allowing for attrition, the trial will recruit and randomise 170 patients.

### 17.1. Statistical Analysis

Data cleaning and analysis will be provided by staff within NCTU and Durham University. Primary analysis will follow intention to treat principles with patient data analysed according to randomisation and irrespective of intervention received; other analysis groups such as per-protocol may be considered subsequently. Every effort will be made to retain and include all patients who are part of the trial.

A full statistical analysis plan (SAP) will be developed for the outcome measures and agreed with the IDMEC and Chief Investigator prior to any analysis being undertaken.

Outcome data will be analysed at the end of the study, no interim analyses is planned.

The primary analysis of presence or absence of cardiac troponin T will be assessed using Fisher's exact test. Analysis of the secondary endpoints will be dependent upon the nature of the specific endpoint and data structure; global longitudinal strain (GLS) and left ventricular ejection fraction (LVEF) will be analysed as a change from baseline using a t-test to compare intervention and control groups.

Cardiac troponin I data will also be analysed using Fisher's exact test. Changes in cardiac troponin T and I will also be analysed as a continuous variable. Additional analysis of the primary endpoint will be performed using logistic regression to account for baseline factors (regimen and HER2 status). Adverse events data will be analysed using cross-tabulation. Sensitivity analysis will also be performed for adherence to the protocol.

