### 9.2. Primary Outcome

The presence ( $\geq 14\text{ng/L}$ ) or absence of cardiac troponin T ( $< 14\text{ng/L}$ ) release at any time during epirubicin treatment, and one month after the last dose of epirubicin.

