### 10.2. Exclusion Criteria

- Positive baseline cardiac troponin T ( $\geq 14\text{ng/L}$ );
- known contraindication to ACE inhibitor e.g. renal artery stenosis, severe aortic stenosis;
- are taking, or have a previous intolerance to ACEI (e.g. angioedema);
- patient already taking other agents acting on the renin-angiotensin-aldosterone system e.g. Aliskiren, angiotensin receptor blockers (ARBs), Entresto (sacubitril/valsartan), spironolactone, eplerenone;
- LVEF  $<50\%$ \*;
- estimated GFR  $< 30\text{ mL/min/1.73m}^2$  at baseline;
- hyperkalaemia defined as serum potassium  $\geq 5.5\text{mmol/L}$ ;
- symptomatic hypotension, or Systolic Blood Pressure  $<100\text{mmHg}$ ;
- poorly-controlled hypertension (Blood Pressure  $>160/100\text{mmHg}$ \*\*, or ambulatory BP of  $150/95\text{mmHg}$ );
- previous myocardial infarction;
- known metastatic breast cancer;
- previous exposure to anthracycline chemotherapy;
- are pregnant or breastfeeding
- Previous Herceptin treatment or planned Herceptin treatment within four weeks following anthracycline chemotherapy
- for patients of childbearing potential: refusal to use adequate contraception throughout the trial;\*\*\*
- any other cancer diagnosis;
- participation in other interventional medicinal trials in the past 6 months;
- judgment by the Investigator that the patient should not participate in the study, for example, if the patient is unlikely to comply with study procedures, restrictions, and requirements.

\*<50% as defined by Simpson's biplane method; if absolute measurements are not possible, then a visually normal assessment of LVEF is acceptable for inclusion.

\*\*White coat hypertension is more common, and should be ruled out by an ambulatory blood pressure monitor

\*\*\*Female patients between the ages of 18 and 50 will receive a pregnancy test at baseline.

Adequate methods of contraception are those that can achieve a failure rate of less than 1% per year when used consistently and correctly, such methods include:

- combined (estrogen and progestogen containing) hormonal contraception associated with inhibition of ovulation
  - oral
  - intravaginal
  - transdermal
- progestogen-only hormonal contraception associated with inhibition of ovulation
  - oral
  - injectable
  - implantable
- intrauterine device (IUD)
- intrauterine hormone-releasing system (IUS)
- bilateral tubal occlusion
- vasectomy/vasectomised partner

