### **11.5. Randomisation**

Randomisation will be performed using a minimisation scheme to ensure patients randomised to each group are comparable at baseline. The minimisation scheme will account for a planned 6 cycle adjuvant chemotherapy regimen (Epirubicin and Cyclophosphamide (EC) or Fluorouracil, Epirubicin and Cyclophosphamide (FEC)), and HER2 (human epidermal growth factor receptor 2) status (positive or negative).

Eligible patients will be randomised by delegated and trained members of the research team at each centre using a 24-hour, central, secure, web-based randomisation system with concealed allocation.

Eligible patients will be randomised in a 1:1 ratio to receive standard care plus enalapril maleate (intervention under study) or standard care (control arm/standard care).

Randomisation system web address:

<https://www.sealedenvelope.com/access/>

This system is available 24 hours a day, 7 days a week.

In the event that the randomisation system is not accessible, the team should contact NCTU staff in normal working hours:

Email: [[contact]](mailto:[contact])

[contact]

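### Baseline troponin T should join regimen and HER2 status in the planned logistic model of the primary outcome; Fisher's exact test can stay primary

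*Combined protocol and SAP*

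**What the plan says.** - Section 9.2 defines a binary primary outcome, troponin T at or above 14 ng/L, as "release at any time during epirubicin treatment, and one month after the last dose of epirubicin".
- Section 10.2 applies the same cut-off at entry. The first exclusion is "Positive baseline cardiac troponin T".
- The assessment table in section 13.1 and the eligibility-sample text in section 13.2.8 show that the baseline sample is taken before randomisation, is used for eligibility, and has its result entered in the eCRF.
- Section 11.5: "The minimisation scheme will account for a planned 6 cycle adjuvant chemotherapy regimen", and for HER2 status. No other factor is listed.
- Section 17.1 (Sample Size) states that "140 patients are needed to detect a reduction in the proportion of patients with cardiac troponin T present from 47% to 20" per cent, using a two-sided Fisher's exact test at 5% with 90% power. 170 are to be randomised to allow for attrition.
- Section 17.1 (Statistical Analysis) makes an unadjusted Fisher's test primary: "The primary analysis of presence or absence of cardiac troponin T will be assessed using Fisher's exact test". It continues: "Additional analysis of the primary endpoint will be performed using logistic regression to account for baseline factors (regimen and HER2 status"). It also plans a continuous analysis of changes in troponin T and I.
- The same section says: "A full statistical analysis plan (SAP) will be developed for the outcome measures". That fuller plan is not among the documents.

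**The concern.** Baseline troponin T measures how far below the outcome threshold each patient starts, so it is the obvious candidate predictor of crossing that threshold later. Yet no named analysis of the binary outcome uses it. Minimisation does not balance it, so a chance difference between arms would be neither prevented by design nor corrected in the adjusted analysis. At stake are the credibility and precision of the adjusted estimate and, to a small degree, power. The data are already collected.

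**Working it through.** **1. The plan's own sample size.** Inputs from section 17.1 (Sample Size): p1 = 0.47, p2 = 0.20, two-sided 5%, 90% power. The mean rate is 0.335 and the difference is 0.27.

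Without continuity correction:
n0 = [1.960 × √(2 × 0.335 × 0.665) + 1.2816 × √(0.47 × 0.53 + 0.20 × 0.80)]² / 0.27² = (1.308 + 0.820)² / 0.0729 = 62.1, so 63 per arm.

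With continuity correction, the usual approximation to Fisher's test:
n = (62.1 / 4) × [1 + √(1 + 4 / (62.1 × 0.27))]² = 69.3, so 70 per arm and 140 in total. The stated figure is reproduced.

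**2. What the planned test delivers.** Full enumeration of the two binomials gives:

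| Patients per arm | Fisher power, 47% v 20% | Chi-square power, 47% v 20% | Fisher size at a common 47% |
|---|---|---|---|
| 70 | 90.8% | 93.4% | 3.4% |
| 85 | 95.4% | 96.7% | 3.8% |

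Fisher's test is conservative, valid and adequately powered on the plan's own inputs.

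**3. Possible size of a chance imbalance.** With 70 per arm, the difference in mean baseline troponin T has standard error √(2/70) = 0.169 SD, so the central 95% range is ±1.96 × 0.169 = ±0.33 SD. At an assumed odds ratio of 2 per SD, an imbalance at that limit shifts the odds ratio by a factor of roughly exp(0.33 × 0.693) = 1.26. At an odds ratio of 3, the factor is exp(0.33 × 1.099) = 1.44. The planned effect is an odds ratio of (0.20/0.80) / (0.47/0.53) = 0.28. Such a shift would not overturn that effect, but it would matter for a smaller one.

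**4. Power gained from the covariate.** Simulation with 140 patients at 47% v 20%, 5,000 trials per setting. Assumptions:
- minimisation on regimen and HER2 status, with probability 0.8 for the better arm;
- regimens split 50/50 and 15% HER2 positive;
- baseline troponin T normal, truncated by the entry rule at +1 or +2 SD;
- half or none of the values at the reporting limit.

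The change in power, for a Firth penalised likelihood-ratio test with baseline troponin T against an unadjusted chi-square test, was:

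| Assumed odds ratio per SD | Change in power (points) |
|---|---|
| 1 | -0.3 |
| 2 | +0.5 to +1.1 |
| 3 | +1.9 to +2.6 |

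A smaller separate simulation (2,000 trials per setting, exactly 70 v 70, cut-off at +1 SD, half at the limit) found about nothing: -0.2 points at odds ratio 2 and -0.1 at 3. The lower end of the range therefore has to be taken seriously.

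A third simulation (10,000 trials) compared the maximum-likelihood model on regimen and HER2 status with the same model plus a standardised baseline value. Likelihood-ratio power went from 93.4% to 93.3% at odds ratio 1 and from 93.3% to 95.2% at 2. Narrowing by the entry rule, or many values at the assay floor, would weaken that gain.

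**5. Precision.** In the maximum-likelihood fit (140 patients, 47% v 20%), the 95% CI half-width for the standardised risk difference is 15.1 points if the covariate is not prognostic, 14.7 to 14.8 at odds ratio 2, and 14.1 to 14.4 at odds ratio 3.

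**6. Choice of fit for the risk difference.** Firth's penalty pulls predicted risks towards one half. At odds ratio 2 the standardised risk difference averaged 26.2 points from the Firth fit, against 27.0 from maximum likelihood. Across settings the pull towards zero was about 0.6 to 0.8 points. That exceeds the half-width gain at odds ratio 2, which is 15.1 - 14.8 = 0.3 to 15.1 - 14.7 = 0.4 points.

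**The case against.** The strongest case against is that nothing is broken. Test and sample size agree, and adjusting for exactly the two minimisation factors is a coherent choice. The covariate's strength is unknown, and entry below 14 ng/L narrows its range. The full SAP is still to be written, so a short protocol paragraph does not prove that the SAP will omit the covariate. All of this stands, and it limits the point to a suggested addition. It does not remove it: covariates have already been named, and the outcome's own baseline is not one of them.

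A reader might infer three stronger things that the documents do not support.

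- *That Fisher's test should be replaced.* Most of the gain from switching comes from leaving Fisher's conservatism. In one setting (140 patients, odds ratio 2) power was 91.5% for Fisher, 93.2% for chi-square and 93.7% for the adjusted Firth test. So 1.7 of the 2.2 points owe nothing to baseline troponin T.
- *That the trial is at risk for smaller effects.* The sample-size section says "a large effect size will be necessary to convince the clinical community to change the pathway of care for these patients", so power for smaller effects was not the design aim.
- *That baseline troponin T goes unused.* It enters implicitly through the continuous analysis of changes; only the binary outcome lacks it.

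**Conclusion.** The point holds as a free improvement to the additional analysis. It is not an error in the primary one. Adding baseline troponin T protects the adjusted estimate against chance imbalance in the outcome's own marker. The expected effect on power is small, about -0.3 to +2.6 points over an unadjusted chi-square test at 47% v 20% with 140 patients. These figures rest on assumed odds ratios of 1 to 3 per SD, an assumed position of the entry cut-off and an assumed share of values at the reporting limit. None of these is in the documents. The facts about what is collected and what is named are firm; the size of the benefit is not.

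**What to change.** Before any outcome data are seen, specify in section 17.1 (Statistical Analysis) or the SAP:

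- The logistic model contains treatment, regimen, HER2 status and baseline troponin T as a continuous covariate. Values below the assay's reporting limit are entered at that limit.
- Report the adjusted odds ratio, and a standardised risk difference with a 95% CI (for example by the delta method or bootstrap), from the maximum-likelihood fit.
- If separation forces Firth's penalised likelihood, do not take the risk difference from uncorrected Firth predictions.
- Fisher's exact test remains primary.

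The cost is wording only. Eligibility depends on the baseline value, so it should exist for every patient properly randomised. Section 13.2.8 withholds end-point troponin results from the research team until the trial ends, so the choice can be made blind to outcomes.

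Making the adjusted model primary is optional and a trade-off. It gives up Fisher's guaranteed 5% bound: simulated type I error with 140 patients was 4.5% to 5.4% for the maximum-likelihood Wald test and 5.0% to 5.9% for the likelihood-ratio test. The sample-size text would need realigning, and the sponsor would have to judge whether section 19.11.2 makes the change a substantial amendment.
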